8.5 Examination of Subgroups

[ICH E3: 11.4.2.8](#); [ICH E9: 5.7](#)

National Institute of Allergy and Infectious Diseases
{Statistical Analysis Plan - Protocol #}

Because of the temporary halt on ICAC-28/CRITICAL study procedures due to the influence of COVID-19, the study population can be divided into two subgroups for the analysis of the primary endpoint.

The first is the group of participants who were expected to follow all guidance per protocol. These participants were expected to reach maintenance-level SCIT/placebo injections within 40 weeks of dose initiation, for example. These participants completed the study prior to the onset of COVID-19 or were enrolled after the restart of study procedures.

The second is the group of participants who were expected to follow guidance in the protocol appendices designed to allow for modifications related to COVID-19. These participants could not be expected to reach maintenance-level SCIT/placebo injections within 40 weeks of dose initiation, for example, because of the period of time in which they could not attend clinic visits. These participants were those already enrolled, but not yet completed, at the onset of COVID-19.

As a sensitivity analysis, the primary endpoint will be calculated by treatment separately for each of the COVID-19 groups above.

9. SAFETY EVALUATION

9.1. Overview of Safety Analysis Methods

The safety analyses will be performed in the safety sample defined in Section 4. Safety assessment summaries will include:

- Adverse events (AEs), defined in Protocol Section 12.2.1.
- Suspected Adverse Reaction (SAR), defined in Protocol Section 12.2.1.1.
- AEs leading to discontinuation of study drug
- Serious adverse events (SAEs), defined in Protocol Section 12.2.3.
- Deaths
- Clinical laboratory results
- Vital signs
- Physical examinations

These analyses will not be stratified by site.

For grading an abnormal value or result of a clinical or laboratory evaluation (including, but not limited to, a radiograph, an ultrasound, an electrocardiogram etc.), a treatment-emergent AE is defined as an increase in grade from baseline or from the last post-baseline value that doesn't meet grading criteria. Changes in grade from screening to treatment initiation at Day 0 will also be recorded as AEs, but are not treatment-emergent.

9.2. Extent of Exposure

[ICH E3: 12.1](#)

9.3. Adverse Events

[ICH E3: 12.2](#)

All AEs will be classified by system organ class (SOC) and preferred term, according to a standardized thesaurus (Medical Dictionary for Regulatory Activities [MedDRA]). The latest edition of MedDRA will be used at the time of classification.

The severity of AEs will be classified, as applicable, using the criteria set forth in the NCI-CTCAE Version 4.03.

Each AE will be entered on the electronic case report form (eCRF) once at the highest severity.

The relationship, or attribution, of an AE to the study therapy regimen or study procedures is defined in Protocol Section 12.3.2.

National Institute of Allergy and Infectious Diseases
{Statistical Analysis Plan - Protocol #}

Overall summary tables will be developed using the Safety Population to report the number of events and the number and percentage of participants having at least one event in the following categories:

- AEs
- AEs by maximum grade
- AEs by relationship to a study drug

AEs classified by treatment arm, MedDRA SOC, and preferred term will be summarized in the Safety Population for each of the following categories:

- AEs
- AEs by maximum grade
- AEs by relationship to study drug

Summary tables will present the total number of events as well as the number and percentage of participants experiencing the events. If a participant experiences the same AE on multiple occasions, the event will be counted once for each occurrence when reporting the number of AEs. When reporting the number of participants experiencing the events, a participant will only be counted once if they experience an event within the particular SOC or preferred term. Percentages will be based on the number of participants in the safety population.

Similar summaries will be generated for SARs (defined in Protocol Section 12.2.1.1) and AEs leading to discontinuation of study drug separately.

Data listings will be provided separately for AEs, SARs, and AEs leading to discontinuation of study drug.

9.4. Deaths, Serious Adverse Events, and Other Significant Adverse Events

ICH E3: 12.3

SAEs will be listed and summarized in the same manner described in Section 8.2. Separate displays listing and summarizing death, including time to death and cause of death, will also be created.

Data listing will be provided separately for SAEs and AEs resulting in death.

9.5. Clinical Laboratory Evaluation

ICH E3: 12.4

Clinical laboratory measurements will be measured at Screening and include IgE. Results will be converted to standardized units where possible. For numeric laboratory results, descriptive

statistics of laboratory values and the change from baseline of laboratory values will be presented for each treatment group and overall. For categorical laboratory results, the number and percentage of subjects reporting each result will be presented for each treatment group and overall.

9.6. Vital Signs, Physical Findings, and Other Observations Related to Safety

ICH E3: 12.5

9.6.1. Vital Signs

Vital sign measurements (including weight in kg, height, pulse rate, respiratory rate, blood pressure, and temperature) and growth parameters will be collected at all E&M visits unless otherwise noted. A data listing of all vital sign and growth parameter measurements will be provided.

9.6.2. Physical Examinations

A study clinician performed a physical examination at Screening visit. A chest auscultation and current asthma symptom assessment were performed at all injection visits. An abbreviated physical examination was performed at all E&M visits. Additional examinations may have been completed at the remainder of the visits at the study clinician's discretion. Significant findings that met the definition of an adverse event (AE) were recorded on the AE form.

9.6.3. Other Safety Measures

Prior to March 16, 2020, peak expiratory flow (PEF) was performed at all clinic visits with the exception of E&M visits. At Screening, Asthma Control, and Randomization visits, this was done to prove asthma control for study eligibility. At injection visits, this was done before and after SCIT injections as a safety measure to ensure no reaction in relation to the treatment. During NAC visits, this was done many times as a safety measure to ensure the challenge was stopped and rescue medications were administered if there were reductions in lung function.

As of June 26, 2020, PEF was replaced during clinic visits with an alternate safety measure, the targeted pulmonary exam. PEF conducted outside of the clinic after NAC visits was replaced with a questionnaire conducted by phone. This decision was made in light of COVID-19 to avoid unnecessary procedures involving forceful exhalation while maintaining assurance of lung function. The frequency of drops in PEF during and after a NAC procedure prior to the onset of COVID-19 were reviewed when considering these alterations.

10. OTHER ANALYSES

10.1. Use of Medications

Medications will be coded according to the World Health Organization (WHO) Drug Dictionary (version 2017.01). Medications reported on the CRF will be categorized for analysis as prior, concomitant, or after study treatment by comparing the medication start and stop dates with the first and last dose of study medication dates. Prior medications will have both the medication start and stop dates prior to the first dose of study medication date. After medications will have both the medication start and stop dates after the last dose of study medication date. All other medications will be classified as concomitant, indicating that use of the medication overlapped with use of the study medication by at least one day.

The number and percentage of subjects receiving prior, concomitant, and after medications will be presented overall and by medication class. When reporting the number of subjects receiving the medication, a subject will only be counted once if they ever received the medication within the medication class. Percentages will be based on the number of subjects in the analysis population.

11. INTERIM ANALYSES AND DATA MONITORING

[ICH E3: 11.4.2.3](#); [ICH E9: 4.5](#)

The progress of the study will be monitored by the Data and Safety Monitoring Board (DSMB). The NIAD Allergy and Asthma DSMB will be chartered to review safety data and to make recommendations regarding continuation, termination, or modification of the study. The DSMB will formally review the safety data at least yearly. The discontinuation of study treatment will also be periodically reported to the DSMB.

In addition, safety data will be reviewed by the DSMB when an event occurs that is of sufficient concern to the National Institute of Allergy and Infectious Diseases (NIAID) medical monitor or protocol chair to warrant review, or when an event occurs that could contribute to a predefined stopping rule specified in the protocol.

Findings will be reported to Institutional Review Boards (IRBs) and health authorities.

12. CHANGES TO THE ANALYSES PLANNED IN THE PROTOCOL

ICH E3: 9.8

The protocol describes the Per Protocol analysis population to be “All participants who are randomized, are escalated to at least 0.4 mL of the 1:10 maintenance dose and receive at least 66% of expected doses of maintenance.”

This analysis plan has changed the definition of the Per Protocol analysis population to be “All participants who are randomized, are escalated to at least 0.4 mL of the 1:10 maintenance dose and receive at least 3 doses of maintenance.” This change was made to simplify the definition due to the pause in immunotherapy caused by the COVID-19 pandemic.

14. APPENDIX

14.1. Table of Estimands

Objective Clinical Category	Statistical Category	Estimand/Variable

Primary Objective: To compare efficacy of cockroach subcutaneous immunotherapy (SCIT) superiority within placebo/active in participants with participants with asthma and german cockroach sensitization with respect to:
		
Efficacy Category 1	Primary/MCP	
• Variable: Change in mean TNSS after 12 months of treatment with cockroach SCIT.• Population: Of all subjects defined by the study inclusion / exclusion criteria, the analysis population will include subjects who are modified ITT and per protocol population.• Intercurrent Event Strategy (IES): All intercurrent events will be handled following hypothetical strategy (imputation). Missing data of this nature, as well as missing data due to withdrawal, will be multiple imputed as described above in section 7.1.3.• Population Level Summary (PLS): Difference between treatment groups, Cockroach SCIT vs Placebo, in the change in mean TNSS after 12 months of treatment between the placebo and treatment arm.• Analysis: The comparison between arms will be conducted using an analysis of covariance (ANCOVA) model, where the change from baseline to 12-month mean TNSS score is the outcome. The ANCOVA model will include fixed categorical effects for treatment and baseline mean TNSS score, with adjustment for site. Least square means (LSmeans) and associated SEs will be presented for each treatment group. The comparison between treatment groups will be presented using the LSmeans difference and associated 2-sided 95% confidence interval (CI) and p-value.

National Institute of Allergy and Infectious Diseases
{Statistical Analysis Plan - Protocol #}

Efficacy Category 2	Secondary/MCP	
Variable: Change in TNSS AUC from baseline to 12 months. AUC at baseline will be calculated from the TNSS score across 9 doses or until reaction (TNSS \geq 6 or sneeze score of 3, whichever occurs first). The TNSS AUC at 12-months will be calculated from the TNSS score across 9 doses or until TNSS = 12 or the baseline reacting dose has been reached, whichever occurs first.For the mITT population, like the rules referenced in section 8.2.1, the TNSS AUC will be calculated separately at baseline and 12 months for each subject using the trapezoidal rule and divided by their baseline reactive dose. Change in TNSS AUC will be compared between treatment arms using an analysis of covariance (ANCOVA) model. The model will contain the change from baseline to 12-month TNSS AUC as the outcome, and fixed effects for baseline TNSS AUC, treatment group, and site. Least square means and associated SEs will be presented for each treatment group. Difference in least square means between treatment groups will be presented along with associated 2-sided 95% confidence interval (CI) and p-value.
	Secondary/MCP	
Variable: Change in Responsive dose from baseline. Responsive dose will be calculated as the first dose for which a reaction (TNSS \geq 6 or sneeze score of 3, whichever occurs first) occurs in the sequence of up to 9 doses.Analysis: For the mITT population, compare the change in responsive dose (the dose which elicits the threshold response of a TNSS \geq 6 or a sneeze score \geq 3) from baseline to the 12-month NAC between treatment groups, using discrete-time (discrete-dose) survival analyses^{1,2}. This analysis, which will estimate a hazard ratio, is based on a model for the conditional probability of a subject reacting to a given dose, given that the subject has not

¹

²

National Institute of Allergy and Infectious Diseases
 {Statistical Analysis Plan - Protocol #}

[figure not shown]
		reacted to previously administered doses. Participants who reach the last dose without reacting will be considered right censored. The baseline NAC responsive dose and site will be controlled and there are no imputations for missing 12-month NAC observations.
	Secondary/MCP	
 Variable: Change in log-transformed German cockroach-specific IgE and IgG4 from baseline to 12 months. Analysis: For the mITT population, 12-month log-transformed IgE and IgG4 will be modeled as ANCOVA with factors for treatment arm, site, and the respective log-transformed baseline as covariates. Geometric least square means (LSmeans) and associated SEs will be presented for each treatment group. The geometric least square mean ratio comparing treatment vs placebo group, associated 95% confidence interval (CI) and p-value will be presented.
	Sensitivity	
 Analysis: For the mITT population, baseline and 12-month log transformed IgE and IgG4 will be modeled using a linear mixed model that will include a random intercept and fixed effects for each treatment arm, site, and an interaction term between treatment arm and time of measurement. Similarly to the ANCOVA, geometric least square means (LSmeans) and associated SEs will be presented for each treatment group. The geometric least square mean ratio comparing treatment vs placebo group, associated 95% confidence interval (CI) and p-value will be presented

Secondary Objective: To compare efficacy of cockroach subcutaneous immunotherapy (SCIT) superiority within placebo/active in participants with participants with asthma and german cockroach sensitization with respect to:
		
Safety Category 1 (e.g., AEs)		
 Variable: Rate of immunotherapy related adverse events and immunotherapy related serious adverse events in the course of treatment Analysis: For the safety samples, the difference in the number and percentage of serious and non-serious adverse events between treatment groups. The analysis will be stratified by grade.

National Institute of Allergy and Infectious Diseases
{Statistical Analysis Plan - Protocol #}

IES = Intercurrent event(s) strategy; PLS = Population-level summary; MCP=Multiple comparisons procedure

All estimand attributes explicitly identified for primary/secondary and select key estimands only.

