8.1.5 Nasal Allergen Challenge

The NAC must be rescheduled if the participant meets the following criteria:

- Has uncontrolled asthma at the time of the NAC, as defined by an $FEV_1 < 80\%$ predicted or an ACT score < 20 .
- Has active rhinitis symptoms at the time of the NAC, defined as a Baseline TNSS > 3 , or any individual symptom score > 1 .
- Is currently using oral or nasal antihistamines, nasal corticosteroids, nasal decongestants, nasal anticholinergics, biologic therapies, prednisone, or cromolyn, which cannot be suspended for the required washout periods.

Baseline peak flow (PEF) and TNSS will be measured before the start of the challenge. Nasal lavage will be performed as described in Section 8.1.6.

Increasing doses of allergen will be administered in defined time intervals (every 10-20 minutes) up to a specified maximum dose or symptom level, will be given as described in an accompanying MOP for Protocol ICAC-28. Briefly, one spray (100mL) of diluent or diluted allergen solution is applied to each of the participant's nostrils using a nasal drug delivery system (LMA/Teleflex, San Diego, CA) while the participant breath-holds at TLC. After the dose is delivered, the participant is asked to exhale through the nose and then to avoid sniffing or swallowing in the immediate 1 minute after application. For the baseline NAC, the challenge will begin with a 0 mcg/ml of Bla g 1 [negative control – 50% glycerin, 50% COCAS with 0.2% phenol (Stallergenes Greer, Lenoir, NC)] dose followed by up to 8 doses of increasing concentration, until the participant reaches a TNSS of 6 or more, has a sneezing score of 3, or their symptoms become intolerable. Collection of TNSS and PEF will be done 10 minutes after each diluent or allergen dose is administered.

The follow-up challenge at 12 months will be performed as described above, except the challenge will continue until the participant reaches at least the dose that elicited a positive response at the baseline NAC or the participant reaches a TNSS of 12 or their symptoms become intolerable. If a participant reaches the dose that elicited a positive response at the baseline NAC without having a TNSS of 6 or more or a sneezing score of 3, dosing will continue until the participant reaches a TNSS of 6 or more, has a sneezing score of 3, or symptoms become intolerable.

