2. PURPOSE OF THE ANALYSES

The purpose of this statistical analysis plan (SAP) is to describe the planned analyses and data displays to be included in the Clinical Study Report (CSR) for Protocol ICAC-28. This document provides details on study populations, how the variables will be derived, how missing data will be handled and details on statistical methods to be used to analyze the safety and efficacy data.

The statistical analysis plan (SAP) is based on ICH guidelines E3 and E9 (Statistical Principles for Clinical Trials).

The document may evolve over time, for example, to reflect the requirements of protocol amendments or regulatory requests. However, the final SAP must be finalized, approved by the Client, and placed on file before database is locked. If differences occur between analyses described in the SAP and the current protocol, those found in this SAP will assume primacy. Deviations from the final approved plan will be noted in the clinical study report.

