8.1.3. Missing Data

The primary method of handling missing efficacy data will be the use of complete case analysis for the primary analyses. Indeed, participants with missing data for the 12 months NAC will not be included in the ANCOVA with factors for arm and site and the respective baseline TNSS as a covariate.

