8.2. Primary Endpoint

[ICH E9: 2.2.2-2.2.7](#)

Variable (Endpoint): Change in mean TNSS after 12 months of treatment with cockroach SCIT.

Population: Of all subjects defined by the study inclusion / exclusion criteria, the analysis population will include subjects who are in the modified ITT and per protocol populations.

Intercurrent events: All intercurrent events will be handled following hypothetical strategy (imputation). Missing data of this nature, as well as missing data due to withdrawal, will be multiple imputed as described above in section 7.1.3.

[figure not shown]
Population-level summary: Difference between treatment groups, Cockroach SCIT vs Placebo, in the change in mean TNSS after 12 months of treatment between the placebo and treatment arm.

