8.2.1. Computation of the Primary Endpoint

The primary endpoint of the study is the change in the mean TNSS from baseline to 12 months, calculated as the difference between the mean TNSS at baseline up to their baseline responsive dose and the mean TNSS at 12 months up to their baseline responsive dose.

Below are a couple of examples describing the above calculations. The top row displays the participant's TNSS scores and bottom row displays the participants sneeze scores. The pink line is the measurement taken at baseline while the blue line is the measurement taken at 12 months.

1. Example

In this example, the participant reacted at baseline with sneeze at dose 6.

The baseline mean TNSS is calculated up to dose 6:

$$\frac{0 + 0 + 0 + 1 + 0 + 3}{6} \approx 0.7$$

The 12-month mean TNSS is calculated the same as the baseline mean:

[figure not shown]
$$\frac{2 + 0 + 0 + 0 + 0 + 0}{6} \approx 0.3$$

Then change in the mean TNSS from baseline to 12 months will be calculated as:

Page 20 of 40

$$0.3 - 0.7 = -0.4$$

2. Example

Unlike the participant in the example above, this participant reacted at baseline with TNSS, dose 4. However, the calculation of the mean and change in mean are similar.

The baseline mean TNSS is calculated up to dose 4:

$$\frac{4 + 4 + 3 + 9}{4} \approx 5$$

The 12-month mean TNSS is calculated the same as the baseline mean:

$$\frac{2 + 2 + 3 + 4}{4} \approx 2.8$$

Then change in the mean TNSS from baseline to 12 months will be calculated as:

$$2.8 - 5 = -2.2$$

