8.3.2. Endpoint 2a

Variable: Change in TNSS AUC from baseline to 12 months, calculated as the difference between the AUC TNSS at baseline up to their baseline responsive dose and the AUC TNSS at 12 months up to their baseline responsive dose.

Analysis: For the mITT population, like the rules referenced in section 8.2.1, the TNSS AUC will be calculated separately at baseline and 12 months for each subject using the trapezoidal rule and divided by their baseline reactive dose. Change in TNSS AUC will be compared between treatment arms using an analysis of covariance (ANCOVA) model. The model will contain the change from baseline to 12-month TNSS AUC as the outcome, and fixed effects for baseline TNSS AUC, treatment group, and site. Least square means and associated SEs will be presented for each treatment group. Difference in least square means between treatment groups will be presented along with associated 2-sided 95% confidence interval (CI) and p-value.

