8.3.3. Endpoint 2b

Variable: 12-Month responsive dose. 12-Month responsive dose will be calculated as the first dose for which a reaction (TNSS ≥ 6 or sneeze score of 3, whichever occurs first) occurs in the sequence of up to 9 doses.

Analysis: For the mITT population, the 12-month responsive dose will be analyzed using a Cox Regression model. This analysis, which will estimate a hazard ratio, is based on a model for the conditional probability of a subject reacting to a given dose, given that the subject has not reacted to previously administered doses. Participants who reach the last dose without reacting will be considered right censored. The baseline responsive dose and site will be controlled and there will be no imputation for missing 12-month NAC observations.

8.3.4. Endpoint 3

Variable: Change in log-transformed German cockroach-specific IgE and IgG4 from baseline to 12 months.

Analysis: For the mITT population, 12-month log-transformed IgE and IgG4 will be modeled as ANCOVA with factors for treatment arm, site, and the respective log-transformed baseline as covariates. Geometric least square means (LSmeans) and associated SEs will be presented for each treatment group. The geometric least square mean ratio comparing treatment vs placebo group, associated 95% confidence interval (CI) and p-value will be presented.

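### SAP 14.1 cuts the 12-month TNSS AUC at TNSS = 12 but divides by the full baseline reactive dose, so the AUC is too low whenever a challenge stops early at the maximum

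*SAP*

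**What the plan says.** - **SAP 14.1 (Table of Estimands), TNSS AUC.** The 12-month AUC is taken "across 9 doses or until TNSS = 12 or the baseline reacting dose has been reached, whichever occurs first". The same cell then divides the area by the baseline reactive dose.
- **SAP 8.3.2 (Endpoint 2a).** The AUC at each visit is calculated "using the trapezoidal rule and divided by their baseline reactive dose". The 12-month range runs to the baseline responsive dose. There is no cut at TNSS = 12 and no rule for doses that were not given.
- **Protocol 8.1.5.** The 12-month challenge goes on at least to the baseline responsive dose, "or the participant reaches a TNSS of 12 or their symptoms become intolerable". It can therefore end before that dose, and no later scores exist.
- **SAP 8.1.5.** TNSS runs from 0 to 12, so 12 is the maximal reaction. This section describes the 12-month challenge without mentioning the early stop.
- **SAP 8.3.2, model.** An ANCOVA on the change in AUC, with baseline AUC, treatment and site, in the mITT sample. SAP section 5 admits a treated, randomized child to that sample after a single dose of the 12-month challenge, so a challenge stopped early qualifies.

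**The concern.** Under SAP 14.1 the area is shortened but the divisor is not. Every dose after an early stop at 12 contributes nothing, as if the child had had no symptoms there, when the challenge ended because symptoms were at the top of the scale. A child who reaches the maximum sooner can then receive a lower 12-month AUC than a child who has not changed at all.

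The responsive-dose endpoint would treat the same child the other way: "12-Month responsive dose will be calculated as the first dose for which a reaction" occurs, so an earlier reaction counts as an earlier event. At stake is whether one secondary endpoint ranks children correctly in exactly the cases where the reaction is strongest.

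**Working it through.** **Conventions assumed.** The reactive dose R is the dose number, doses are one unit apart, and area starts at dose 1. The SAP gives no worked AUC, so these follow the divisors in its worked means.

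**The plan's own figures (SAP 8.2.1, Example 2).** Baseline (4+4+3+9)/4 = 5.0. At 12 months (2+2+3+4)/4 = 2.75, printed as 2.8. The unrounded change is -2.25; the SAP prints -2.2 from rounded means. The divisor is the dose number, 4.

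**AUC formula.** Sum of (s_i + s_(i+1))/2 over the doses counted, divided by R. Change = 12-month minus baseline.

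**Baselines.**
- Example 2 (4,4,3,9): 4 + 3.5 + 6 = 13.5; 13.5/4 = 3.375.
- Example 1 (0,0,0,1,0,3): 0.5 + 0.5 + 1.5 = 2.5; 2.5/6 = 0.417.
- An assumed baseline near the planning mean of 2.94 in protocol 13.6 (1,2,3,6; mean 3.0): 1.5 + 2.5 + 4.5 = 8.5; 8.5/4 = 2.125.

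**12-month paths.** All are assumed except 2,2,3,4, which is the SAP's own. The last column completes the series with all remaining scores 0 (lower end) or all 12 (upper end).

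| Baseline | 12-month path | AUC under SAP 14.1 | Change | Change if completed |
|---|---|---|---|---|
| 4,4,3,9 | 2,2,3,4 | 8/4 = 2.0 | -1.375 | complete |
| 4,4,3,9 | 4,4,3,12 | 15/4 = 3.75 | +0.375 | complete |
| 4,4,3,9 | 4,4,12 | 12/4 = 3.0 | -0.375 | +1.125 to +2.625 |
| 4,4,3,9 | 2,2,12 | 9/4 = 2.25 | -1.125 | +0.375 to +1.875 |
| 4,4,3,9 | 2,12 | 7/4 = 1.75 | -1.625 | -0.125 to +4.375 |
| 1,2,3,6 | 1,2,12 | 8.5/4 = 2.125 | 0.0 | +1.5 to +3.0 |
| 0,0,0,1,0,3 | 0,0,0,1,12 | 7/6 = 1.167 | +0.75 | +1.75 to +2.75 |

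For 4,4,12, adding a dose-4 score z gives an area of 12 + (12+z)/2. That is 18 (4.5) at z = 0 and 24 (6.0) at z = 12, so the wrong sign does not depend on carrying 12 forward. The order is also wrong: a 12 at dose 4 scores +0.375, and a 12 one dose earlier scores -0.375.

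**General shortfall.** The least area that can be missing after a stop at dose k is (12+0)/2 = 6; the most is 12(R-k). Divided by R, the shortfall lies between 6/R and 12(R-k)/R: 1.5 to 3.0 for R = 4, k = 3. It is never zero.

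**When the sign reverses.** Let b denote the baseline scores. A child who repeats them through dose R-2 and reaches 12 at dose R-1 has an area difference of (12 - b(R-1))/2 - (b(R-1) + b(R))/2. This is negative when 2b(R-1) + b(R) > 12. Example 2: 6 + 9 = 15, reversed. Baseline 1,2,3,6: 6 + 6 = 12, exactly zero. Example 1: 0 + 3 = 3, not reversed. For Example 1, any 12 at dose 2 or later has an area of at least 6, so the score is at least 6/6 = 1.0, above 0.417.

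**Changing only the divisor to the doses given.** 4,4,12: 12/3 - 3.375 = +0.625. 2,12: 7/2 - 3.375 = +0.125. 2,2,12: 9/3 - 3.375 = -0.375, although every completion of that path gives an AUC of at least 15/4 = 3.75.

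**The case against.** **The model does not use the sign of one child's change.** With baseline AUC as a linear covariate, the treatment estimate is the same whether the outcome is the change or the 12-month value. This stands, and it rules out reading the table as children being classified as improved. It does not remove the fault. At the same baseline, the child with 4,4,12 still enters with 3.0, below the 3.375 of an unchanged child.

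**The reversal depends on an unusual baseline.** Example 2's mean of 5.0 is (5.0 - 2.94)/1.09 = 1.89 SD above the planning mean. Near that mean the comparable path scores 0.0, and Example 1 does not reverse for stops at dose 2 or later. A TNSS of 12 also needs all four symptoms at their maximum. This stands for the sign, but not for the understatement, which occurs at every such stop.

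**SAP 8.3.2 does not score missing doses as zero.** Correct: it is silent, and the zero area comes from SAP 14.1 alone. The rule that, where SAP and protocol differ, "those found in this SAP will assume primacy" cannot choose between two sections of the SAP.

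**AUC and responsive dose may legitimately diverge.** They are different constructs, so disagreement alone proves nothing. Here, though, it can come from the scoring rather than from the child's response.

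**The primary mean.** A reader might infer that the primary endpoint has the same fault. The documents do not support that. SAP 8.2.1 takes "the mean TNSS at 12 months up to their baseline responsive dose" and does not address a truncated challenge, while protocol 13.4.2 averages over the doses observed. Silence in the SAP is not a difference that displaces the protocol.

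**Conclusion.** The point holds for SAP 14.1 as written: the 12-month TNSS AUC is too low, by between 6/R and 12(R-k)/R, whenever the challenge stops at TNSS = 12 before the baseline reacting dose. SAP 8.3.2 does not agree with 14.1 and does not settle how such a challenge is scored. A wrong sign is possible but only for some baselines.

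The figures rest on the dose number as divisor, unit spacing, area from dose 1, and assumed 12-month paths.

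A reader might go on to infer that the AUC comparison is biased for or against SCIT. That cannot be said: the documents give no frequency of early stops, overall or by arm, so neither the size nor the direction of a trial-level effect can be stated. One secondary endpoint is affected; the primary sample size and power are not. It should be fixed because a stated rule gives a wrong score in a planned situation and the correction is small.

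**What to change.** - Align SAP 8.3.2 and 14.1. When the 12-month challenge stops at TNSS = 12 before the baseline responsive dose, carry 12 forward to that dose for the AUC and keep the baseline-dose divisor. Changing the divisor alone is not sufficient in all cases.
- Report the number of early stops by arm and reason.
- For the primary mean, only confirm in SAP 8.2.1 that the protocol's average over observed doses applies to a truncated challenge.

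The cost is SAP wording and a few lines of AUC programming. The drawback is that 12 is the upper limit for the doses not given and a single filled-in value ignores uncertainty: for 4,4,12 it gives +2.625, where +1.125 to +2.625 is possible. The count of early stops lets the reader judge how much rests on this. SAP section 2 allows changes until database lock; a later change would have to be noted in the study report as a deviation.
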